### 10.2 Best Response

Best response is defined as the best measured response (CR, CRp, CRI, PR, or NR) over all response assessments at all time points after the start of study treatment.

## **11. STATISTICAL ANALYSES**

An outline of the statistical and pharmacokinetic analyses is provided below. Details will be specified in the Statistical Analysis Plan.

### **11.1 Analysis Sets**

The sponsor will finalize the population flag of individual patients for each analysis set after CRF lock. Patients with major Good Clinical Practice (GCP) violations (eg, a violation of the informed consent procedure, a major violation of study procedures) will be excluded from all analysis sets and be assessed individually. Patients with a quizartinib dose reduction for any reason after the start of study treatment will be analyzed as patients at the dosing level at the start of study treatment.

The sponsor will also finalize the population flag of patients who are not specified in the protocol or the Statistical Analysis Plan based on the advice of the medical expert as needed.

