### **5.3.4 Randomization and Blinding**

Neither randomization or blinding will be used in the study.

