#### **11.1.1 Safety Analysis Set**

The Safety Analysis Set is defined as patients who received at least 1 dose of any of the study drug, cytarabine, and the anthracycline drug.

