#### **11.1.3 MTD Analysis Set**

The MTD Analysis Set is defined as patients who received at least 1 dose of any of the study drug, cytarabine, and the anthracycline drug, but excludes the patients listed below.

- Patients whose DLT assessment has not been performed appropriately because some of the procedures during the DLT assessment period are missing for other reasons than adverse drug reactions (eg, worsening of the clinical condition due to progression of the primary disease, AEs that are assessed as not related to the study drug)
- Patients who have taken quizartinib for the following number of days during the DLT assessment period
  - The number of days of quizartinib administration is  $\leq 9$  for patients who have

completed remission induction therapy in Cycle 1

- The number of days of quizartinib administration is  $\leq 9$  both in Cycle 1 and Cycle 2 for patients who have proceeded to remission induction therapy in Cycle 2.

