#### **11.3.2 Safety Analysis**

Other safety analyses than DLT analyses will be performed on the Safety Analysis Set, whereas DLT analyses will be performed on the MTD Analysis Set.

AEs that occur or worsen relative to the pre-treatment state after the start of study treatment (treatment emergent AEs [TEAEs]) will be tabulated. AEs collected in the study will be coded using the Medical Dictionary for Regulatory Activities (MedDRA) terminology developed by the International Conference on Harmonisation of Technical Requirements for Registration of Pharmaceuticals for Human Use (ICH), and be

tabulated by body organ group using the MedDRA system organ class (SOC) and by AE term using preferred terms (PT).

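### Section 11.1 removes patients with major GCP violations, including an undefined class of major procedure violations, from every analysis set, so a dosed patient can be missing from the primary safety and DLT tables

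*Combined protocol and SAP*

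**What the plan says.** Section 11.1 (Analysis Sets) opens with a rule that governs all the sets defined after it. It covers "Patients with major Good Clinical Practice (GCP) violations (eg, a violation of the informed consent procedure", followed by the second example, "a major violation of study procedures) will be excluded from all analysis sets and be assessed individually". It gives no definition of *major*, and no method, listing or table for the individual assessment. On timing and responsibility it says: "The sponsor will finalize the population flag of individual patients for each analysis set after CRF lock". Section 5.3.4 adds: "Neither randomization or blinding will be used in the study".

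The definitions that follow are more inclusive. Section 11.1.1 takes into the Safety Analysis Set "patients who received at least 1 dose of any of the study drug, cytarabine, and the anthracycline drug", with no exclusion of its own. Section 11.1.3 starts from the same dosed patients and removes two groups from the MTD Analysis Set: those with too few quizartinib days, and those whose DLT assessment was compromised because procedures were "missing for other reasons than adverse drug reactions".

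Section 11.3.2 ties the tables to these sets: "Other safety analyses than DLT analyses will be performed on the Safety Analysis Set", whereas "DLT analyses will be performed on the MTD Analysis Set". The Synopsis lists safety (AEs, laboratory data, vital signs, body weight, ECG) among the primary endpoints. Section 11 describes itself as an outline and leaves detail to a Statistical Analysis Plan. Nothing in the document as supplied returns an excluded patient to a table.

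**The concern.** A safety population normally holds everyone who was exposed, because the question is what happened to the people who took the treatment. Section 11.1.1 follows that principle and Section 11.1 then sets it aside. A violation of procedures does not undo exposure, and an AE or a QTcF value above 500 ms in such a patient is still information about the regimen.

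The class of patients removed has no stated boundary, and the flags are finalized when outcomes can be known. That implies no bad intent, but the plan offers no protection against a classification influenced by what happened to the patient.

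With 3 or 6 patients per level, a single flag matters. The table that supports the primary objective could show a different number of DLTs, out of a different number of patients, from the count on which the dose was chosen.

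**Working it through.** **Inputs.** Section 11.5 and its rationale: at least 3 patients per level, up to 3 more per level after a DLT, 6 to 12 in all. Tables 5.4-1 and 5.4-2: 0/3 stops the level at three, 1/3 adds three patients, and 2/3 or 3/3 stops the level. Section 11.1: flags are finalized after CRF lock, so after enrollment at every level has ended.

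**The plan's own figure.** Two levels: 3 × 2 = 6 and (3 + 3) × 2 = 12. The stated range of 6 to 12 is reproduced.

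**Share of one patient.** With no replacement patients, 1/3 = 33% of a level that stops at three and 1/6 = 17% of an expanded level. Over the whole study it is 1/12 = 8% to 1/6 = 17%.

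**Effect on a reported DLT count.** Suppose a level closes with x DLTs in n patients and one patient is then removed. If that patient had a DLT, the table shows (x − 1)/(n − 1). If not, it shows x/(n − 1).

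| Count at the dose decision | Patient with a DLT removed | Patient without a DLT removed |
|---|---|---|
| 1/6 (17%) | 0/5 (0%) | 1/5 (20%) |
| 2/6 (33%) | 1/5 (20%) | 2/5 (40%) |
| 3/6 (50%) | 2/5 (40%) | 3/5 (60%) |
| 2/3 (67%) | 1/2 (50%) | 2/2 (100%) |

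In the first row, removing the patient with the DLT leaves no DLT in the table. In the third row, Table 5.4-2 reads 3 of 6 at Level 2 as an MTD of 20 mg. The reported number of events would then be 2, the largest number it reads as 40 mg among six patients, over a denominator of 5 that no row covers. The same algebra applies to any AE term (11.3.2.1, 11.3.2.2) and any QTcF category (11.3.2.6).

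**Can the escalation process absorb this?** The MTD is decided during the study under Sections 5.4.2 to 5.4.4, before the flags of Section 11.1 exist. The text under Table 5.4-2 asks that AEs in patients excluded from DLT assessment be considered, but only at Level 1, only for exclusions under Section 5.4.4, and only for the decision to proceed. It puts nobody back into a table.

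**Do the DLT rules agree with one another?** Not fully. Section 5.3.2 excludes any patient with a quizartinib overdose in the DLT period from DLT assessment. Section 5.4.4 does so only if additional enrollment is decided, and also lists ineligibility and withdrawal. Section 11.1.3 mentions none of these three. Even without the blanket rule, then, the MTD set may differ from the patients used for the decision.

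**The case against.** The strongest case against the point is about scope. The trigger is a major *GCP* violation, and Section 15.8 names that separately from a significant protocol deviation. Narrower rules already handle the obvious candidates. Overdose affects DLT assessment only (5.3.2, 5.4.4). Drugs that prolong QT and strong CYP3A4 inhibitors are allowed for infection when medically essential, with quizartinib interrupted (5.7). Missing procedures or too few dosing days affect the MTD set only (11.1.3). If every such event were a major GCP violation, the missing-procedure rule in 11.1.3 would be largely redundant. The category is also prespecified, with only the individual flags coming late, and in an open-label study outcomes are known before lock too. The patients' AEs remain in the CRF and SAEs are reported within 24 hours.

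Most of this stands, and it rules out several stronger inferences.

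- A reader might infer that a level with 1 DLT in 3 could be reported as 0/2. The plan does not lead there: 1/3 brings in three more patients before any flag is finalized, so the level holds six. Reaching 0/2 would require abandoning the expansion, which Section 5.4.2 does not describe.
- A reader might infer that the rule biases toxicity rates downward. It does so only when the excluded patient had the event. Otherwise the rate rises, or stays at zero if there were no events.
- A reader might infer that dosing errors, prohibited drugs or missed ECGs would lead to exclusion from all sets. Section 11.1 names none of them. Section 1.3.2 reports torsades de pointes in a patient taking a strong CYP3A4 inhibitor, so a link between such a violation and toxicity is plausible. Its classification as major is still an assumption.

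The objection does not answer the central point: whatever *major* is taken to mean, the patients it covers leave the Safety Analysis Set.

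**Conclusion.** The point holds as a defect in the definition of the analysis sets. As written, Section 11.1 can take a dosed patient out of the primary safety tables and the DLT table, against the all-dosed definition in 11.1.1. One exclusion costs 17% of an expanded level or 33% of a level that stops at three. It changes the reported DLT proportion in either direction, depending on whether that patient had a DLT.

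This rests on two assumptions: at least one dosed patient with valid consent is judged to have a major violation, and the separate Statistical Analysis Plan does not narrow the rule. How often the first would happen cannot be estimated from the documents. A reader might infer that the MTD could be altered, but the documents do not support that. The effect is on the reported tables, which may fail to match the decision, and on how completely they describe exposed patients. The correction is cheap and should be made; the design does not depend on it.

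**What to change.** In Section 11.1, limit removal from all analysis sets to patients whose data may not be used, that is, those without valid consent. State that every other dosed patient stays in the Safety Analysis Set.

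For the MTD Analysis Set, let only the DLT-evaluability criteria in Section 11.1.3 decide membership, after reconciling them with Sections 5.3.2 and 5.4.4. Apply them in the same way whether or not a DLT occurred. Keeping violators only when they had a DLT would make membership depend on the outcome and could push the rate up. The aim is an MTD set identical to the patients used for the dose decision.

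List each excluded patient, with reason, AEs and any DLT, beside the tables.

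The cost is one sentence in 11.1, a reconciliation of the evaluability criteria and one listing. Sample size and study conduct do not change. The downside is that the safety tables will include patients with procedure violations, who can be flagged in a listing.

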## **5.4 Assessment of Dose-limiting Toxicity**

### **5.4.1 Definition of Dose-limiting Toxicities**

The DLT assessment period is from the start day of quizartinib administration in Cycle 1 of remission induction therapy to the preceding day of Day 1 of Cycle 1 of consolidation therapy (induction phase), and a DLT is defined as any toxicity among AEs that occur during the above period that are assessed to be “related” to quizartinib, as listed below. The severity grade will be assessed according to the Common Terminology Criteria for Adverse Events (CTCAE) v4.0 Japanese version.

- $\geq$  Grade 3 non-hematological toxicities (except for the following)
  - Alopecia, anorexia, and fatigue
  - Grade 3 queasy, vomiting, or diarrhea that has improved to  $\leq$  Grade 2 within 7 days after the onset after treatment with antiemetic or antidiarrheal drugs
  - Grade 3 mucositis that has improved to  $\leq$  Grade 2 within 7 days after the onset
  - Grade 3 infections
  - Febrile neutropenia
- Hematological toxicities that have not resolved before Day 1 of Cycle 1 of consolidation therapy, as listed below
  - Peripheral neutropenia ( $< 500/\text{mm}^3$ )
  - Thrombocytopenia resulting from bone marrow aplasia or hypoplasia ( $< 20\,000/\text{mm}^3$ )

- $\geq$  Grade 3 thrombocytopenia associated with bleeding ( $< 50\ 000/\text{mm}^3$ )
- Grade 4 thrombocytopenia requiring blood transfusion ( $< 25\ 000/\text{mm}^3$ )

If there is a day when quizartinib cannot be taken due to any toxicity during the DLT assessment period, the investigator and the sponsor will discuss and decide whether to handle the toxicity as a DLT or not.

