**Table 5.4-2 Criteria for Assessing Maximum Tolerated Doses (MTDs) at Level 2**

Incidence of DLTs in the first 3 patients at Level 2, and the decision	Incidence of DLTs when 3 patients are additionally enrolled at Level 2 (a total of 6 patients), and the decision
0 of 3 patients: Terminate the study (MTD: 40 mg).	—
1 of 3 patients: Additionally enroll 3 patients at Level 2.	1 of 6 patients or 2 of 6 patients: Terminate the study (MTD: 40 mg). 3 of 6 patients or 4 of 6 patients: Terminate the study (MTD: 20 mg).
2 of 3 patients or 3 of 3 patients: Terminate the study (MTD: 20 mg).	—

If any of the criteria provided in “5.4.4 Enrollment of Additional Patients” is met at Level 1 and any patient is excluded from DLT assessment, information on AEs occurring in the concerned patient, etc. should be taken into consideration to assess whether to proceed to Level 2 or not.

Whether it is necessary or not to establish a new level, in addition to Level 1 and Level 2, will be determined through discussion between the investigator and the sponsor. The medical expert will be consulted as needed.

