## **5.5 Criteria for Temporary Discontinuation, Dose Reduction, and Resumption of Quizartinib**

- When the need arises to use drugs that may potentially prolong the QT/QTc interval or strong CYP3A4 inhibitors by necessity during the quizartinib treatment period: Quizartinib administration should be temporarily discontinued from the start to the end of use of the above-mentioned drugs. On the day when the quizartinib is resumed after interruption, vital sign measurement, 12-lead ECG, and laboratory tests will be performed before the start of quizartinib administration (refer to “6.2 Remission Induction Therapy” and “6.3 Consolidation Therapy”).
- When  $\geq$  Grade 3 QTcF prolongation occurs in a patient at Level 2: Quizartinib administration should be temporarily discontinued from the onset time of the above event.  
If the increase in QTcF recovers to  $\leq$  30 ms, compared with the value at registration, within 14 days after the onset, quizartinib administration will be resumed at a dose reduced to 20 mg/day.  
If the increase in QTcF does not recover to  $\leq$  30 ms, compared with the value at registration, within 14 days after the onset, the study for the relevant patient will be discontinued.  
\* If  $\geq$  Grade 3 QTcF prolongation occurs in a patient at Level 1, the study for the patient should be discontinued (refer to “5.6 Withdrawal Criteria”).
- When a DLT occurs (including cases in which it takes time to assess the causality with quizartinib, cytarabine, or the anthracycline drug but the toxicity can potentially be associated with quizartinib):  
If Grade 3 non-hematological toxicity (except QTcF prolongation) occurs during the induction phase and it is assessed to be “related” to quizartinib, quizartinib administration will be temporarily discontinued from the onset time of the event. If

the event resolves to Grade 1 within 28 days after the onset of the event and the investigator or subinvestigator decides it possible to resume quizartinib administration, quizartinib administration will be resumed.

If a Grade 4 non-hematological toxicity (except QTcF prolongation) occurs during the induction phase, the study for the relevant patient will be discontinued.

Once the dose of quizartinib is reduced, the dose should not be increased again to the original dose.

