## **5.7 Prohibited Concomitant Drugs and Therapies, Restricted Concomitant Drugs, and Drugs to Be Coadministered with Care**

Prohibited concomitant drugs and therapies:

Concomitant use of the following drugs, etc. is prohibited during the quizartinib

treatment period.

As an exception, the drugs listed in 1) and 2) may be used only when the investigator or subinvestigator considers that these drugs are medically essential to prevent or treat infection. In this case, oral treatment with quizartinib should be interrupted from the start to the end of use of the drugs listed in 1) and 2), and be resumed on the following day of the end of use of the drugs. At the time of resumption, no dose reduction of quizartinib will be necessary unless the investigator or subinvestigator considers it necessary.

- 1) Drugs that may potentially prolong the QT/QTc interval
- 2) Strong CYP3A4 inhibitors
- 3) Strong or moderate CYP3A4 inducers
- 4) Crude drugs and food products with CYP3A4-inhibiting or -inducing properties (eg, foods and beverages containing St. John's wort or grapefruit)
- 5) Anticancer treatments other than quizartinib (except hydroxycarbamide)
- 6) Investigational drugs other than quizartinib, and investigational devices
- 7) Donor lymphocytes

Restricted concomitant drugs:

The following treatments should be restricted during oral treatment with quizartinib:

- Treatment with hydroxycarbamide for control of the white blood cell count:  
Restricted to a daily dose of 2 g for up to a total of 14 days

[Drugs to be coadministered with care]

During oral treatment with quizartinib, use of substrates and inhibitors of P-glycoprotein should be avoided as far as possible.

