## 6.7 Pharmacokinetics

After 2 mL of blood is collected from each patient, as specified in “Table 6.7-1 Blood Collection Points for Pharmacokinetic Assessment,” the plasma specimens will immediately be stored in a frozen state at  $-90^{\circ}\text{C}$  to  $-70^{\circ}\text{C}$ . The specimens in a frozen state will be submitted to the agency contracted by the sponsor to collect the specimens. Details including the handling of specimens will be specified in separate procedures. The date and time of blood collection will be recorded in the CRF.

Table 6.7-1 Blood Collection Points for Pharmacokinetic Assessment

Treatment Cycle	Treatment Day	Blood Collection Point (Acceptable Limit)
Remission induction therapy	Day 8 * First day of quizartinib administration	Pre-dose 30 minutes ( $\pm 10$ minutes) post-dose
Cycle 1		1 hour ( $\pm 10$ minutes) post-dose 2 hours ( $\pm 10$ minutes) post-dose 4 hours ( $\pm 10$ minutes) post-dose 6 hours ( $\pm 10$ minutes) post-dose
	Day 9	Pre-dose
	Day 15	Pre-dose 2 hours ( $\pm 10$ minutes) post-dose 4 hours ( $\pm 10$ minutes) post-dose

	Day 21 * Last day of quizartinib administration	Pre-dose 30 minutes ( $\pm$ 10 minutes) post-dose 1 hour ( $\pm$ 10 minutes) post-dose 2 hours ( $\pm$ 10 minutes) post-dose 4 hours ( $\pm$ 10 minutes) post-dose 6 hours ( $\pm$ 10 minutes) post-dose
	Day 22	On the specified day
	Day 28	On the specified day
Consolidation therapy Cycle 1	Day 6 * First day of quizartinib administration	Pre-dose 2 hours ( $\pm$ 10 minutes) post-dose 4 hours ( $\pm$ 10 minutes) post-dose
	Day 7	Pre-dose
	Day 13	Pre-dose 2 hours ( $\pm$ 10 minutes) post-dose 4 hours ( $\pm$ 10 minutes) post-dose
	Day 19 * Last day of quizartinib administration	Pre-dose
	Day 28 (-3 days to the day)	On the specified day

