### **15.3 Procedures for Informed Consent**

The investigator or subinvestigator will explain the details of the study listed below to subject candidates in a readily understandable way using the informed consent documents, before any invasive procedures related to the study are performed in each subject, and obtain written informed consent to participate in the study by their free will. Before obtaining consent, the investigator or subinvestigator should give the subject

candidates ample time and opportunity to ask questions to decide whether to participate in the study, and should answer the questions in an appropriate manner.

Before the start of study drug administration in Cycle 1 of consolidation therapy, written informed consent to continue participation in the study after the end of the DLT assessment period will be obtained again from the subjects. For subjects who experienced any DLTs during the DLT assessment period, written informed consent to continue participation in the study will be obtained again before resuming the study drug administration after recovery from the toxicity.

The investigator or subinvestigator who has provided an explanation and the subject who has given consent will sign and date the consent form. If study staff personnel provide a supplementary explanation to the subject candidates, the study staff should sign and date the form. The investigator or subinvestigator will provide a copy of the consent form along with the subject information form to the subject, and retain the original consent form at the study center. The investigator or subinvestigator will document (eg, in the original consent form or medical record) that a copy of the consent form and subject information form have been provided to the subject.

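### The starting-level rule in 11.1 has no PK exception, so a Level 2 patient reduced to 20 mg has later PK data summarised as 40 mg

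*Combined protocol and SAP*

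**What the plan says.** **Assignment rule.** Section 11.1, ahead of the five set definitions: "Patients with a quizartinib dose reduction for any reason after the start of study treatment will be analyzed as patients at the dosing level", meaning the level they began on. Nothing in 11.1.4 (PK Analysis Set) modifies this. That set needs only one dose, specimens and available measurements.

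**How a reduction arises.** Under 5.5, a Level 2 patient with QTcF prolongation of Grade 3 or higher is held. On recovery within 14 days, "quizartinib administration will be resumed at a dose reduced to 20 mg/day". The change is permanent: "Once the dose of quizartinib is reduced, the dose should not be increased again to the original dose". Section 15.3 confirms that a patient with a DLT may restart, since "written informed consent to continue participation in the study will be obtained again before resuming the study drug administration after recovery from the toxicity". Section 5.7 gives a second route. After a hold for a prohibited drug, "no dose reduction of quizartinib will be necessary unless the investigator or subinvestigator considers it necessary".

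**What is sampled later.** Section 7 derives Cmax,ss, Ctrough, Tmax,ss and AUCtau,ss from induction Cycle 1 Day 21, with no condition on the dose received. "Table 6.7-1 Blood Collection Points for Pharmacokinetic Assessment" (Section 6.7) also schedules samples on Days 6, 7, 13, 19 and 28 of consolidation Cycle 1.

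**How it is summarised.** The synopsis groups concentrations by dose level and 11.3.4 groups them by dose. Neither says assigned or actual. Sections 7 and 11 defer details to a SAP, whose text is not in the supplied file. Section 11.2 lets the sponsor decide the handling of individual data before lock.

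**The concern.** Analysing by starting level is a normal choice for safety, DLT and efficacy, where the question is what happens to patients started at a dose. A PK summary describes the exposure that a dose produces. Applied there, the rule puts concentrations produced wholly or partly by 20 mg into the 40 mg column. Because reductions only go down, the effect always understates 40 mg exposure, and it adds spread that comes from dosing history. PK in Japanese patients is a primary endpoint and part of the primary objective, and each level has only 3 to 6 patients, so one profile carries weight in the reported summary.

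**Working it through.** The documents give no figure on this point to reproduce. The sizes below are illustrative.

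**Inputs**
- Dosing on Days 8–21 of induction Cycle 1, 14 doses (5.3.1).
- Half-life about 3 days and accumulation about 4-fold (1.3.4). With r = 2^(−1/h), accumulation is 1/(1 − r): 4.0 at h = 2.41 d and 4.8 at h = 3 d. I use h = 2.41, 3 and 3.5 d.
- Dose proportionality, stated for 30–90 mg (1.3.4). Its extension to 20 mg is an assumption.
- Hold lengths are assumptions. One-compartment superposition is assumed.
- Level size: a related Grade 3 QTcF event is not among the exceptions in 5.4.1, so it is a DLT, and Table 5.4-2 says "1 of 3 patients: Additionally enroll 3 patients at Level 2". Hence n = 6.

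**Day 21 AUCtau relative to uninterrupted 40 mg**

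f = Σ dose_d · r^(21−d) ÷ Σ 40 · r^(21−d), summed over Days 8–21. The shift in the arithmetic mean of 6 is (1 − f)/6.

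| Last 40 mg dose, first 20 mg dose | f at h = 2.41 / 3 / 3.5 d | Mean of 6 lower by |
|---|---|---|
| Day 8, Day 12 (3-day hold) | 0.486 / 0.480 / 0.474 | 8.6–8.8% |
| Day 15, Day 19 (3-day hold) | 0.457 / 0.480 / 0.497 | 8.4–9.0% |
| Day 15, Day 21 (5-day hold) | 0.290 / 0.327 / 0.354 | 10.8–11.8% |
| Day 8, Day 21 (longest hold) | 0.133 / 0.118 / 0.110 | 14.4–14.8% |

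**Against sampling error.** The standard error of a 6-patient mean is 40%/√6 = 16% to 70%/√6 = 29% at an assumed CV of 40–70%. All the shifts are smaller.

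**Consolidation Cycle 1.** Day 6 falls at least 13 days after induction Day 21, so r^13 = 2–8% carries over. Post-dose concentrations are then about 0.50 of those on 40 mg, and the mean of 6 is lower by 0.50/6 = 8.3% if all six reach consolidation, or by more if fewer do. This applies whenever in induction the reduction happened.

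**Frequency.** Table 1.3-1 shows QTcF > 500 ms in 5% at 30 mg and 3% at 60 mg, on continuous dosing in a different setting.
- First 3 at Level 2: 3 × 0.03 = 0.09 to 3 × 0.05 = 0.15 patients expected.
- Six at Level 2: 6 × 0.03 = 0.18 to 6 × 0.05 = 0.30.
- Fewer still for the Day 21 parameters, which also require recovery, renewed consent and a restart by Day 21.

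No size is claimed for the 5.7 route, since the documents give no frequency for it.

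**Would regrouping Day 21 by dose taken work?** In the 5-day case, 56–73% of the Day 21 AUCtau comes from the earlier 40 mg doses, yet the profile is only 2f = 0.58–0.71 of uninterrupted 20 mg. Added as a fourth profile to three full 20 mg profiles, it would lower that mean by (1 − 0.71)/4 = 7% to (1 − 0.58)/4 = 10.5%. It is a steady-state profile for neither dose.

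**The case against.** The strongest reply is that 11.1 assigns a patient to a level but does not oblige every profile to enter every summary. A SAP could leave an interrupted or reduced Day 21 profile out of the steady-state table without contradicting 11.1, and 11.2 gives the sponsor a mechanism for isolated anomalies. That stands for Day 21. It does not remove the point, because 11.2 sets no PK rule and a decision taken near data lock is weaker than a prespecified one.

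It can also be said that 11.3.4, the specific PK section, groups by dose, and that this can mean dose taken. This stands as an ambiguity, and it matters most for consolidation, where Section 7 derives no parameters and only concentrations are tabulated. But the synopsis says dose level and 11.1 fixes a reduced patient's level at the start, so two of the three places point to the 40 mg label.

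The case is also rare and its effect lies within sampling noise. That is correct and sets the severity.

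Two stronger readings are tempting and not supported:
- A reader might infer that the dose decision is biased. Escalation and MTD in Section 5.4 rest on DLT counts, not on PK means.
- A reader might infer that the plan is also wrong to call Day 21 values steady state after holds without a reduction. That rests only on silence, on a matter deferred to the SAP, and is not claimed here.

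**Conclusion.** The point holds as a low-severity labelling problem in a primary-endpoint summary. As written, 11.1 and the synopsis place post-reduction PK data from a Level 2 patient under 40 mg, and no supplied text makes an exception. The wording in 11.3.4 leaves room for the opposite reading, so this is a conflict to reconcile and not proof that the analysis will be mislabelled.

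The effect is conditional on an uncommon event (0.09–0.15 expected among 3 patients, 0.2–0.3 among 6). When that event occurs, the 6-patient mean Day 21 AUCtau falls by about 8–12%, or up to about 15% at the extreme, and consolidation means fall by about 8% if all six contribute. These sizes rest on the one-compartment model, the assumed holds, proportionality down to 20 mg and an arithmetic mean of six. Day 8 parameters are unaffected. The QTcF reduction route exists only at Level 2, because Level 1 patients with such an event leave the study (5.5, 5.6).

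**What to change.** Change the PK analysis only; no dosing, hold or withdrawal rule is touched.

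1. Add a PK exception to 11.1 so that data obtained after a dose reduction are not summarised as 40 mg, and align the synopsis and 11.3.4 with it.
2. Tabulate consolidation Cycle 1 concentrations by the dose actually taken.
3. Leave Day 21 profiles obtained after a reduction out of both the 40 mg and the 20 mg steady-state summaries. Flag and list them individually, and show the all-patient starting-level summary alongside.
4. Keep the starting-level rule for safety, DLT and efficacy.
5. If the SAP or the handling under 11.2 already does this, cite it in 11.1.4.

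The cost is about one sentence each in 11.1, 11.1.4 and 11.3.4, wording aligned in the synopsis, and one extra summary column. Doses, dates, interruptions and reductions are already recorded in the CRF (6.2, 6.3). The downside is that the steady-state summary may rest on fewer patients and may select on exposure, since patients held for QTcF may be those with high concentrations. That is why the all-patient summary stays beside it.
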